4. STUDY ENDPOINTS

4.1 Primary Endpoints

- Safety: subject incidence of adverse events, DLTs, and clinically significant changes in vital signs, ECGs, physical examination findings, and clinical laboratory tests

4.2 Secondary Endpoints

- PK of AMG 211 after cIV infusion across 2 cycles
- Incidence of anti-AMG 211 antibody formation
- Time to progression
- 6-month progression-free rate
- Efficacy parameters: overall response rate (ORR; per modified irRC), duration of response, time to response

4.3 Exploratory Endpoints

- Changes in methylation and mutations in circulating free DNA present in plasma
- Lymphocyte counts, T-cell activation and immune checkpoint regulator status

- Changes in serum cytokine levels
- Biomarkers and mutations in tumor cells
- Changes in CTCs
- sCEA serum levels

5. HYPOTHESES AND/OR ESTIMATION

The hypothesis for this phase 1 study is that objective responses according to modified irRC will be observed at dose levels that achieve acceptable safety and tolerability.

6. DEFINITIONS

Adverse Event (AE)

An adverse event is defined as any untoward medical occurrence in a clinical trial subject. The event does not necessarily have a causal relationship with study treatment. The definition of adverse events includes worsening of a preexisting medical condition. Worsening indicates that the preexisting medical condition (eg, diabetes, migraine headaches, gout) has increased in severity, frequency, and/or duration, and/or has an association with a significantly worse outcome. A preexisting condition that has not worsened during the study, or involves an intervention such as elective cosmetic surgery or a medical procedure while on study, is not considered an adverse event.

Age at Enrollment

Subject age at enrollment will be determined using the age in years reported in the clinical database.

AUC_{inf}

Area under the concentration-time curve from time zero to infinity.

Baseline

Unless otherwise specified, the baseline value for parameters/assessments scheduled to be performed on the same day as the first administration of AMG 211, is the last value measured before the first administration of AMG 211 on that day. For parameters/assessments not scheduled to be performed (or scheduled but not performed) on the same day as the first administration of AMG 211, the baseline value is the value from the screening period measured

closest to the day of first administration of AMG 211. In the event that multiple assessments are done on the same day as the first administration of AMG 211 and there is no time associated with the assessments, the value associated with the last clinically planned event before the first administration of AMG 211 will be used as the baseline value.

Best Overall Response

Best overall response for a subject is the best observed post baseline disease response per modified Immune-Related Response Criteria (irRC). Any irCR or irPR must be confirmed by consecutive repeat assessments performed at least 4 weeks after the criteria for response are first met. The confirmatory scan can also be performed at the next scheduled imaging visit. An irPD must be confirmed by consecutive repeat assessments performed at least 4 weeks apart in the absence of rapid clinical deterioration. The confirmation scan may also be performed at the next imaging assessment as defined by the schedule of assessment after the first observation if the subject has stable or improved clinical status. Subjects with a global deterioration of health status requiring discontinuation of treatment without objective evidence of disease progression at the time should have the reason for treatment discontinuation classified as non-confirmed disease progression. The investigator reported response information collected on the CRF and/or Independent review committee assessments will be used to determine the response.

Change From Baseline

Change from Baseline is the arithmetic difference between post-Baseline and Baseline.

C_{ss}

Steady-state drug concentration in serum calculated as average concentration between achievement of plateau and EOI during constant-rate infusion.

Complete Response

Complete response is defined using the modified irRC as outlined in Appendix D of the protocol.

Dose Limiting Toxicity (DLT)

Please refer to section 6.2.1.3 in the protocol for definition of DLT.

Duration of Response

Duration of response is defined as the number of days between the date of the first tumor assessment indicating an objective response through to the subsequent date of progression as classified by modified irRC or death due to any cause, or where applicable date of censoring [date of first progressive disease assessment or death or date of censoring – date of the first objective response result +1]. Subjects who respond and have not progressed while on study or died for reasons other than disease progression will be censored at the date of assessment of the last evaluable radiological assessment. Subjects who do not achieve an objective response will be excluded from the analysis of duration of response.

End of Investigational Product Administration

End of IP Administration for each subject is defined as the date the decision was made to end IP as recorded on the End of IP CRF page.

End-of-Study

The end of study date for an individual subject is recorded on the end of study CRF page. End of study (EOS) for an individual subject is defined as the date of the final study visit (EOS visit) when safety assessments and procedures are performed. The EOS visit should occur approximately 4 weeks (+ 1 week) after the last dose of AMG 211 or at the initiation of other therapy. Subjects who complete the EOS visit will be considered to have completed the study. Primary Completion: the time when the last subject is assessed or receives an intervention for the purposes of final collection of data for the primary analysis; the primary analysis for this study will occur after all dose-escalation cohort subjects and dose-expansion cohort subjects have completed 6 months of treatment or have discontinued treatment with AMG 211.

End of Trial: the time when the last subject is assessed or receives an intervention for evaluation in the study; the final analysis will occur at this time.

Enrollment

A subject is considered enrolled on day 1 (cycle 1 day 1) when the cIV infusion with investigational product is first administered. See protocol section 5.0 for further details.

Fridericia-corrected QT Interval (QTcF)

The Fridericia correction will be calculated from the investigator reported QT (msec) and RR interval (msec), as follows:

$$QTcF=QT/(RR/1000)^{1/3}$$

Investigational Product

The term 'investigational product' is used in reference to AMG 211.

Last Investigational Product Dose Date

The last IP dose date for each subject is defined as the latest date IP is administered.

Maximum Tolerated Dose (MTD)

Given the toxicity probability interval (TPI) specified, after each cohort, the model's recommended MTD dose for evaluation is the dose with the highest probability of the target TPI, but with a less than 0.25 probability of an excessive or unacceptable TPI. The actual dose selected at each dose decision may be at or below the model's recommended dose as determined at a DLRM by the dose level review team (DLRT) after considering all information.

A final model estimate of the MTD will be obtained utilizing all the dose-escalation cohort and dose-expansion cohort DLT-evaluable subjects.

Percent Change From Baseline

Percent change from Baseline is the arithmetic difference between post-Baseline and Baseline divided by Baseline values times 100.

Progression-Free Survival Time

Progression-free survival time is calculated as the number of days from the first administration of AMG 211 to the first assessment of disease progression as per modified irRC or clinical progression, whichever occurs first or death due to any cause, or if applicable date of censoring (date of progressive disease or death or censoring – date of study day 1 +1). Progression-free Survival Time will incorporate the independent radiologic review and/or the Investigator-reported assessment. The progression-free rate at 6 months is defined as the proportion of subjects with no disease or clinical progression at 6 months from the first administration of AMG 211.

The following censoring strategies for missing assessment dates will be used for the progression free survival analysis:

If a subject's disease has not progressed and the subject is alive, progression-free survival time will be censored at the last date they are known to be progression-free (ie, the last evaluable radiological assessment date).

If a subject has no tumor evaluation in the study, progression-free survival time will be censored at the date of the first administration of AMG 211.

Subjects who withdraw consent to participate in the study prior to disease progression will be censored at their last evaluable radiological assessment date.

Screened

A subject is considered in screening once a consent form has been signed.

Study Day

Post study day 1: study day= (date - date of Study Day 1) + 1

Pre study day 1: study day= (date – date of Study Day 1)

Study Day 1

Study day 1 is defined as the first day of administration of the investigational product after enrollment. The day prior to Study Day 1 is considered Day -1.

Treatment-Emergent Adverse Event (TEAE)

A treatment-emergent adverse event is any adverse event starting on or after the first dose of investigational product, as determined by the flag indicating if the adverse event started prior to the first dose on the Adverse Events Summary CRF, and up to and including 30 days after the end of investigational product.

Treatment-Related AE

A treatment-related AE is any treatment-emergent AE that per investigator review has a reasonable possibility of being caused by the investigational product.

Time to Progression (TTP)

Time to progression is calculated as the number of days from the first administration of AMG 211 to the first objective assessment of disease progression as per modified irRC or if applicable date of censoring (date of progressive disease or censoring – date of study day 1 +1). Time to progression will incorporate the independent radiologic review and/or the Investigator-reported assessment.

The following censoring strategies for missing assessment dates will be used for the time to progression analysis:

If a subject's disease has not progressed and the subject is alive, time to progression will be censored at the last date they are known to be progression-free (ie, the last evaluable radiological assessment date).

If a subject has died, time to progression will be censored at the date of death.

If a subject has no tumor evaluation in the study, progression-free survival time will be censored at the date of the first administration of AMG 211.

Subjects who withdraw consent to participate in the study prior to disease progression will be censored at their last evaluable radiological assessment date.

Time to Response

Time to response is calculated as the number of days from the first administration of AMG 211 to the first objective assessment of response as per modified irRC or if applicable date of censoring (date of first response or censoring – date of study day 1 +1).

The following censoring strategies for missing assessment dates will be used for the time to response analysis:

If a subject did not respond, time to response will be censored at the latest evaluable radiological assessment date.

If a subject has no tumor evaluation in the study, time of response will be censored at the date of the first administration of AMG 211.

Tumor Burden

Tumor burden is derived as the sum of the products of the 2 longest perpendicular diameters (SPD) of all index lesions (5 lesions per organ and up to 10 total lesions) and new measurable lesions ($\geq 5 \times 5$ mm; up to 5 new lesions per organ and 10 total lesions) if any, per irRC guidelines.

- Tumor burden = $SPD_{\text{index lesions}} + SPD_{\text{new, measurable lesions}}$

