6.2.1.1 Dosage, Administration, and Schedule

AMG 211 will be delivered using preprogrammed infusion pumps approved for use by the appropriate regulatory authority for the country in which the subject is undergoing treatment.

AMG 211 infusion for solution will be prepared in bags for IV infusion. The investigational product will be administered as a cIV infusion at a constant flow rate over 1 to 4 weeks followed by a 3-week (cohort 1 in the dose-escalation cohorts) or 2-week

(all other cohorts) treatment free interval prior to the following treatment cycle. Subjects will be hospitalized on day 1 cycle 1 for a minimum of 72 hours and at all subsequent cycles for a minimum of 48 hours. Subjects can be hospitalized for a longer time period at the discretion of the investigator. If required for logistical reasons (eg, long travel times), subjects may be hospitalized the day before dosing (day -1) of any cycle and at the EOI for cycle 1 for required PK samples. Subjects in the 7- and 14-day schedules will receive AMG 211 for 7 or 14 days followed by 21 days off or 14 days off, respectively (a 28-day cycle). Subjects on a 28-day schedule will receive AMG 211 for 28 days followed by 14 days off (a 42-day cycle).

The planned dose levels for the dose-escalation cohorts are: 200, 400, 800, 1600, 3200, and 6400 µg/d. Alternative dose levels up to 12800 µg/day will be explored in either 14-day or 28-day schedule based on emerging data. The MTD or recommended phase 2 dose will be administered in the dose-expansion cohort.

The infusion start time should be chosen carefully to avoid any interference or inconvenience with time points of safety assessments, PK/PD measurements, and infusion bag changes. The site should record any unscheduled interruption of an infusion on the eCRF, and provide the start and stop date/time of the infusion and the bag change.

AMG 211 should be administered through a central venous access. In the event that administration through a central venous access is not possible, AMG 211 may be administered temporarily through a peripheral venous line if the subject is hospitalized. The final solution for infusion should be administered through a 0.2 µm in-line filter.

Administration of the premedication (eg, dexamethasone) to minimize the risk of cytokine-release syndrome symptoms is recommended for all treatments at a dose of 800 µg/day or higher (see [Section 6.5](#)).

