6.5 Concomitant Therapy

Throughout the study, subjects should be encouraged to remain well hydrated throughout the treatment period.

Investigators may prescribe any concomitant medications or treatments deemed necessary to provide adequate supportive care except for those listed in [Section 6.7](#).

Concomitant therapies are to be collected from informed consent, through the EOS. For

all concomitant therapies collect therapy name, indication, dose, unit, frequency, route, start date, and stop date.

Oxygen administration as supportive measure is permitted during study treatment.

For symptomatic treatment of fever > 38.5°C metamizole as infusion and/or paracetamol, ibuprofen, or acetylsalicylic acid are recommended.

Patients should be closely monitored for any signs and symptoms that may be associated with CRS such as pyrexia, headache, nausea, vomiting, asthenia, hypotension, hypoxia and tachycardia during the initiation of AMG 211 treatment. To mitigate the CRS risk prophylactic treatment with steroids (dexamethasone) is recommended to be administered before the first dose (initial cycle) of AMG 211, and before subsequent cycles of AMG 211 (if clinically indicated). **In the event of CRS, an unscheduled blood sample should be collected to measure cytokine levels.**

- The sponsor may recommend treating subjects with prophylactic dexamethasone according to the following: Dexamethasone at a dose of 8 mg or equivalent corticosteroid will be administered
 - 8 to 12 hours prior to the start of the infusion on day -1
 - 1 hour prior to the start of the infusion on day 1
 - Every 8 to 12 hours after start of infusion on days 1 and 2
- Corticosteroid treatment can be continued if deemed necessary by the investigator and after consultation with the sponsor but doses should be tapered as quickly as feasible. Further variations may be needed that should be discussed and agreed upon in a Dose Level Review Meeting (DLRM).

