7.2.1 Screening

After written informed consent has been obtained, subjects will be screened in order to assess eligibility for study participation. The total screening window is up to 21 days, unless otherwise noted. The screening period starts on the day that informed consent is obtained. If a subject has not met all eligibility criteria at the end of the screening period, the subject will be registered as a screen failure. Subjects who screen fail may be eligible to re-screen per the investigator's discretion. Laboratory assessments used to determine subject eligibility may be repeated once for confirmation during each screening period before the subject is considered a screen failure. The subject must be re-consented if a re-screening attempt occurs outside the screening period.

The following procedures are to be completed during the screening period at the time points designated in the Schedules of Assessments ([Table 6](#), [Table 7](#), and [Table 8](#)).

- Confirmation that the ICF has been signed
- Demographic data including sex, date of birth, race, and ethnicity will be collected in order to study their possible association with subject safety
- Clinical evaluation
 - Physical examination as per standard of care (including medical/surgical history). Physical examination findings should be recorded on the appropriate eCRF.
 - Karnofsky Performance Status
 - Height and weight
- Vital signs (ie, blood pressure, heart rate, respiratory rate, temperature)
- Pulse oximetry
- ECG triplicate measurement
- Laboratory assessments: hematology, chemistry, coagulation, urinalysis, serum pregnancy test (females only), hepatitis serology, HIV, and tumor markers
- Biomarker assessments: CTCs, immune cells, **soluble DNA markers**, archival tumor tissue, core biopsy (if required)
- sCEA sample collection
- Imaging assessments (**magnetic resonance imaging [MRI]** or **computed tomography [CT]**) within 28 days prior to study day 1
- Disease assessment based on modified irRC ([Appendix D](#))
- Serious adverse event reporting
- Documentation of concomitant and rescue medications. All prior cancer treatment therapies will be collected, and other prior therapies that were being taken within 30 days preceding start of study treatment should be collected. For prior therapies, collect therapy name, indication, dose, unit, frequency, start date, and stop date.
- Collection of archived tumor tissue or new biopsy (imaging guided eg, ultrasound).

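### In premedicated subjects the SAP's day-1 baseline is drawn after dexamethasone, so later changes in lymphocytes, glucose and immune cells can mix steroid washout with AMG 211 effect

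*SAP*

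**What the plan says.** **Baseline rule.** Under SAP section 6 (Baseline), when a parameter is scheduled on the day AMG 211 starts, its baseline "is the last value measured before the first administration of AMG 211 on that day". Only when nothing is scheduled or done that day does the fallback apply, and then "the baseline value is the value from the screening period measured" nearest to the first administration.

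**Steroid schedule.** Protocol 6.5 says the sponsor may recommend dexamethasone 8 mg, or an equivalent, "8 to 12 hours prior to the start of the infusion on day -1", then "1 hour prior to the start of the infusion on day 1", then every 8 to 12 hours on days 1 and 2. It may be continued if needed.

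**Who receives it.** Protocol 6.2.1.1 says premedication "is recommended for all treatments at a dose of 800 µg/day or higher". Protocol 6.5 recommends steroid before the first dose in the initial cycle and names no dose threshold.

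**Analyses that use the baseline.** SAP 10.5.2.1 plans laboratory grade shifts from baseline. Lymphocytes and glucose are both analytes in protocol Table 9. SAP 4.3 lists "Lymphocyte counts, T-cell activation and immune checkpoint regulator status" and serum cytokine changes as exploratory endpoints, and SAP 10.7 allows plots of biomarker change from baseline.

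**The concern.** The baseline rule is written as if the day-1 pre-dose sample were untreated. In a premedicated subject it is free of AMG 211 but not of steroid. The documents do not treat dexamethasone as inert: it was introduced in the first-in-human study for presumed inflammatory or cytokine-mediated toxicity (protocol 2.2.4). It therefore acts on the biology that the pharmacodynamic endpoints measure, since protocol 2.2.1 describes AMG 211 as causing T-cell activation, proliferation and cytokine release.

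If the steroid depresses circulating lymphocytes at the baseline draw, recovery after day 2 will resemble T-cell expansion due to AMG 211, and a real later fall will look smaller than it is. If it raises glucose at that draw, a real later rise will be understated. The SAP has no steroid exception to the baseline rule, no stratification by premedication and no sensitivity analysis. It states that it was written for the protocol dated 24 March 2014; the present premedication wording came in with Amendment 3, dated 10 May 2016.

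**Working it through.** The plan states no figure to reproduce. The check is of timing, then of size under a stated assumption.

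**1. Which sample is the baseline.** Protocol Tables 6 to 8 schedule hematology, chemistry, immune cells and serum markers before dosing on cycle 1 day 1. The SAP rule therefore selects that sample for all four, and the screening value is used only if the day-1 sample was missed.

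**2. Where it falls relative to dexamethasone.** The first steroid dose is on day -1 and the baseline sample is on day 1, so the sample follows at least 8 mg. If it is drawn within the last hour before infusion, it follows 8 + 8 = 16 mg. Protocol 7.2.2 orders pre-dose assessments relative to AMG 211 only, so the order relative to the second steroid dose is open.

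**3. Whether a pre-steroid sample exists.** Protocol 7.2.1 collects hematology and chemistry at screening, and also "Biomarker assessments: CTCs, immune cells" and soluble DNA markers. Serum markers, which carry the cytokines, are not in that list; their first scheduled sample is day-1 pre-dose.

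**4. Who would be affected.** Table 3 gives 3 to 6 subjects per cohort.
- Reading 6.2.1.1 (800 µg/day or higher): 5 of 7 dose levels, cohorts 4 to 8, 5 × 3 = 15 to 5 × 6 = 30 subjects. Cohorts 1 to 3, 3 × 3 = 9 to 3 × 6 = 18 subjects, fall outside it.
- Reading 6.5 alone (no threshold): all 8 numbered cohorts, 8 × 3 = 24 to 8 × 6 = 48 subjects, with no split by dose.

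Neither count includes the 28-day cohorts X-1 and X-2 or the expansion cohort. Both assume that the recommendation is followed.

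**5. Size.** Let the steroid-free level be L, the steroid fall at the baseline draw be s, and the true AMG 211 change at a later, steroid-free time be t.

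Apparent change = L(1 + t) / [L(1 − s)] − 1 = (1 + t)/(1 − s) − 1.

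The documents give no value for s, so the range is assumed:

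| Assumed s | No drug effect (t = 0) | True 40% fall (t = −0.40) |
|---|---|---|
| 0% | 0% | −40% |
| 10% | 1/0.90 − 1 = +11% | 0.60/0.90 − 1 = −33% |
| 30% | 1/0.70 − 1 = +43% | 0.60/0.70 − 1 = −14% |
| 50% | 1/0.50 − 1 = +100% | 0.60/0.50 − 1 = +20% |
| 60% | 1/0.40 − 1 = +150% | 0.60/0.40 − 1 = +50% |

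For a parameter that the steroid raises by g, such as glucose, a subject with no drug effect later shows 1/(1 + g) − 1. For g = 10%, 25% and 50% that is −9%, −20% and −33%.

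**6. The same subject on days 1 and 2.** While the steroid effect persists at the same level and t = 0, change from the day-1 baseline is 0%, but change from screening is (1 − s) − 1 = −s. Each baseline is therefore clean for one period and contaminated in the other.

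**The case against.** **The bias may not follow dose.** A reader might infer that low-dose cohorts have clean baselines and higher-dose cohorts altered ones, so that the artefact imitates a dose-response. The documents do not support that. The 800 µg/day threshold stands in 6.2.1.1 but not in 6.5. It arrived with Amendment 3, when about 32 subjects had already been treated at up to 6400 µg/day (protocol 2.2.4), and nothing shows which of them received steroid. Premedication is recommended, not required. This objection stands.

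**The effect size comes from outside the documents.** This also stands: the range is an assumption and includes zero. Nor does protocol 6.7 supply evidence of an effect, since the corticosteroid use it lists with immunosuppressive therapies is chronic, not a short prophylactic course.

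**The main results do not depend on it.** Correct. DLTs are defined by absolute counts or toxicity grade, so DLT counts and the TPI model do not change, and response and progression use imaging. The SAP's grade 3 or higher listing shows all of a subject's values for that parameter, concomitant medications are listed by subject, and the biomarker plots are optional. The grade-shift tables are firmly planned, however, and they do use the baseline.

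**Replacing the baseline would import the opposite error.** A reader might infer that the screening value should simply take over. Step 6 shows why not: steroid continues on days 1 and 2, so change from screening would credit the steroid effect to AMG 211. Screening can also be up to 21 days old, while exclusion 4.2.11 bars earlier cancer therapy only within 14 days of study entry. This stands against replacement, but not against a second baseline shown beside the first.

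**Conclusion.** The point holds in a limited form. In any subject premedicated on the protocol 6.5 schedule, the SAP baseline for lymphocytes, glucose and immune cells is a post-dexamethasone value, and the SAP makes no allowance for it. Changes measured after the steroid course ends can combine washout with drug effect. This touches the planned laboratory grade shifts, which serve the primary safety endpoint, and the exploratory pharmacodynamic displays.

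The size is unknown. The apparent rise of 0% to 150% with no drug effect rests on an assumed baseline fall of 0% to 60% and full recovery by the later sample. Alignment with dose is possible but not shown; 6.2.1.1 and 6.5 need to be reconciled before anyone can say which subjects are affected by design. DLT counts, the TPI model, ORR and TTP are untouched. This is a worthwhile, inexpensive improvement to the analysis, not a flaw in the dose-finding.

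**What to change.** In the SAP:

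1. Keep the day-1 pre-dose baseline.
2. For premedicated subjects, add a second set of change-from-baseline and CTCAE-shift summaries for lymphocytes, glucose and immune cells, taken from the last value before the first steroid dose. That is the screening sample already collected.
3. Present laboratory and pharmacodynamic change displays by premedication status.
4. For serum cytokines, which have no screening sample, present results by premedication status and state that no pre-steroid value exists. Moving that draw ahead of the day -1 dose would change the visit schedule, because admission on day -1 is optional.
5. State that day 1 and 2 changes are read against the day-1 baseline, and that later changes are read against both.

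In the protocol, reconcile the premedication wording of 6.2.1.1 with that of 6.5. Which wording should prevail is a clinical decision outside this point.

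**Cost.** SAP text and some extra tables, with no new samples. The screening value may be up to 21 days old, and day 1 and 2 changes from it will include the steroid effect.

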10.6 Efficacy Analyses

Statistical analyses of efficacy endpoints will be considered exploratory. Efficacy data will be conducted on the Safety Analysis Set. Dose/exposure-response relationship may be explored graphically.

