10.6.4 Progression Free Survival

The proportion of subjects that are progression free at 6 months with corresponding exact 80% CI will be calculated using the Clopper-Pearson method. Subjects treated at MTD will be included for this analysis.

Kaplan Meier curve will also be presented as a sensitivity analysis with estimates for rates and 80% CI if subjects come off study prior to 6 months for reasons besides disease progression.

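### The SAP makes death a PFS event but leaves it out of the 6-month progression-free rate, so read literally a death without recorded progression is scored as progression-free

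*SAP*

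**What the plan says.** The entry for Progression-Free Survival Time in SAP Section 6 runs from first dose to progression by modified irRC or "clinical progression, whichever occurs first or death due to any cause". Later in the same paragraph the 6-month rate is defined: "The progression-free rate at 6 months is defined as the proportion of subjects with no disease or clinical progression at 6 months", counted from first dose. Death is not named there.

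Two of the PFS censoring rules that follow matter here. The first requires survival: "disease has not progressed and the subject is alive, progression-free survival time will be censored" at the last evaluable scan. The second does not: "If a subject has no tumor evaluation in the study, progression-free survival time will be censored at the date of the first administration".

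SAP 10.6.4, headed Progression Free Survival, analyses the rate as a proportion with an exact 80% Clopper-Pearson interval and adds "Subjects treated at MTD will be included for this analysis". A Kaplan-Meier curve is a sensitivity analysis "if subjects come off study prior to 6 months for reasons besides disease progression". Protocol 10.4.3.3 also specifies the Clopper-Pearson proportion and says nothing about deaths.

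Time to progression (TTP) is a separate SAP entry. It runs "to the first objective assessment of disease progression as per modified irRC" and censors deaths at the date of death.

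**The concern.** A binomial proportion has no censoring: every subject in the denominator is a success or a failure. If only disease or clinical progression makes a failure, a subject who dies first with neither recorded falls on the success side. The PFS definition a few lines above, and the Kaplan-Meier analysis built on it, put the same subject on the failure side. The main and sensitivity analyses of one endpoint would then classify one death in opposite ways.

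Such deaths are foreseeable. Eligibility asks for a life expectancy of at least 3 months (Protocol 4.1.7). Follow-up scans come every 8 to 10 weeks, or every 10 to 12 weeks on the 28-day infusion, and progression needs confirmation at least 4 weeks later (Protocol 7.3.6). At stake is an upward bias in a named secondary endpoint, estimated in a small group.

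**Working it through.** **Method check.** The documents state no figure for the 6-month rate, so the interval method was checked on their ORR examples. The two-sided 80% Clopper-Pearson limits for x of n are the 0.1 quantile of Beta(x, n−x+1) and the 0.9 quantile of Beta(x+1, n−x).
- 8/39 = 20.5%: 12.3% to 31.2%, as in Protocol 10.2.
- 2/10 = 20.0%: 5.45% to 44.96%, against 5.4% to 45.0% in SAP 3.2; agreement to rounding.

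**Number treated at MTD (n).**
- SAP 3.1 and 3.2: up to 10 expansion subjects plus 3 to 6 at that level in escalation, so 10 + 3 = 13 to 10 + 6 = 16.
- n = 10 arises only if fewer are treated at MTD, for example 7 in expansion plus 3 in escalation.
- Protocol 3.1: about 39 expansion subjects. About 29 of them are Imaging Study subjects who may receive a lower dose, which leaves 39 − 29 = 10 assigned to the MTD or recommended phase 2 dose. If all 39 are at MTD and 6 come from escalation, the maximum is 39 + 6 = 45.

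**Shift in the rate.** Let s be the number alive and progression-free at 6 months and d the deaths by 6 months with no progression of either kind recorded. The literal definition gives (s + d)/n; death as failure gives s/n. The difference is d/n. For d = 1:
- n = 10: 1/10 = 10.0 points
- n = 13: 1/13 = 7.7 points
- n = 16: 1/16 = 6.3 points
- n = 45: 1/45 = 2.2 points

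**Examples with 80% intervals** (s and d are assumptions):

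| n | Death as failure | Literal, d = 1 |
|---|---|---|
| 10 | 2/10 = 20.0% (5.5 to 45.0) | 3/10 = 30.0% (11.6 to 55.2) |
| 13 | 3/13 = 23.1% (8.8 to 44.4) | 4/13 = 30.8% (14.2 to 52.3) |
| 16 | 3/16 = 18.8% (7.1 to 37.1) | 4/16 = 25.0% (11.4 to 43.9) |
| 45 | 9/45 = 20.0% (12.4 to 29.7) | 10/45 = 22.2% (14.3 to 32.2) |

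Two such deaths at n = 10 would give 4/10 = 40.0% (18.8 to 64.6).

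**Day-1 censoring.** Suppose one subject dies before any scan and is censored at first dose, and nobody else is censored. Kaplan-Meier PFS at 6 months becomes s/(n − 1) instead of s/n: 2/9 = 22.2% against 20.0% at n = 10, and 3/15 = 20.0% against 18.8% at n = 16. The main proportion does not use this rule and is unchanged by it.

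**The case against.** The strongest reply is that the SAP never says a death is a success. The rate sits inside the PFS entry, directly after death is named as an event, and is analysed under a PFS heading. A programmer could derive it from the PFS variable and score deaths as failures. That is fair: a reader might infer that the SAP deliberately counts deaths as successes, and the documents do not support that inference. What stands is that the rate has its own definition, that definition omits death, and nothing elsewhere supplies it.

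A second defence treats the rate as a TTP quantity, since Protocol 1.2 pairs the two and TTP censors deaths. This fails. The SAP rate includes clinical progression, which TTP does not, and a simple proportion cannot censor anyone.

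Third, the Kaplan-Meier sensitivity analysis would count such a death as an event. It would expose a discrepancy, but it would not correct the main figure.

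Fourth, few subjects may be affected. Deaths after recorded clinical progression are already failures. The end-of-study visit comes about 4 weeks after the last dose and no survival follow-up is scheduled, so some later deaths may never be recorded. This limits the likely size without changing the direction.

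Fifth, on day-1 censoring, the PFS formula applies censoring only where applicable, and the list is introduced as dealing with missing assessment dates. The ordinary reading is that a recorded death is an event. The missing survival condition is therefore a wording conflict, and it would be wrong to infer that it distorts the main rate.

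**Conclusion.** The point holds as a defect in the written definition. Applied as worded, the 6-month rate scores a death without recorded progression as progression-free, against the PFS definition in the same entry and against the sensitivity analysis.

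The size is 1/n per such death. This assumes that at least one occurs, which the documents neither show nor exclude. The one-death shifts in the examples stay within the wide 80% intervals, but they go only upward.

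A reader might infer that the rate will be materially inflated, or that the trial's conclusions are compromised. Neither is supported. There is no death count to work from, the primary endpoint is safety, no dose or stopping rule uses this rate, and SAP 10.6 states "Statistical analyses of efficacy endpoints will be considered exploratory". The change should be made because the rate is a named secondary endpoint and its classification of deaths should not be left to inference. The day-1 censoring wording is minor.

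**What to change.** In SAP Section 6, define the 6-month progression-free rate as the proportion of subjects alive without disease or clinical progression at 6 months from first dose, with deaths counted as failures. Keep the Clopper-Pearson proportion as the main analysis in SAP 10.6.4.

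As a minor correction, restrict the PFS rule that censors at first dose to subjects who are alive and have no tumor evaluation. Only the Kaplan-Meier sensitivity analysis is affected.

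Optionally, state how unknown 6-month status is classified. SAP 10.6.2 already counts unevaluable subjects as non-responders for ORR. With 2 known progression-free and 1 unknown among 10, the rate is 2/10 = 20.0% if the unknown is a failure, 2/9 = 22.2% if excluded and 3/10 = 30.0% if a success. Counting unknowns as failures is conservative; the price is a downward bias for subjects who leave early.

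The two corrections cost a few words of SAP text and no protocol change. Compared with the literal reading, naming death leaves the reported rate the same or lower.
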